#### 6.6 Data Management

Data analysts and research coordinators will collect data and record it in a custom-designed computer database. Data abstraction from electronic medical records will employ either standardized paper data sheets or a custom-designed interface maintained within Intermountain's secure Research Electronic Data Capture (REDCap) platform. Outside REDCap, all study data will be kept in a protected database on a protected computer. Each subject will be assigned a study identification number, and we will maintain minimal patient identifiers. Data for analysis will use study ID codes for patient subjects. Shared or presented data will be in anonymized or aggregate format such that individual patient subjects cannot be reidentified. Any hard copy case report forms will only include study identification numbers, and will be stored in a locked file cabinet.

## 7. DATA ANALYSIS

#### 7.1 Introduction to Quasi-Experimental Analysis

This study will measure the effect of implementing a teambased Code Sepsis protocol for ED sepsis patients by comparing risk-adjusted process and patient-centered outcomes before versus after protocol implementation at a single hospital. Results from simple pre/post analyses, however, may be subject to misinterpretation due to *secular trends* (changes in the measured outcomes over time not attributable to the study intervention). Analyses of Aim III primary and secondary outcomes will therefore employ quasi-experimental methods to eliminate confounding due to secular trends when estimating the effect of Code Sepsis implementation on outcomes. More complex methods of quasi-experimental analysis includes interrupted time series

Figure 4. Difference-in-differences analysis

and regression discontinuity, but are analogous to the relatively simpler approach called *difference-in-difference analysis* (Figure 4). Difference-in-difference analysis uses multivariable linear regression to compare the adjusted mean door-to-antibiotic time (primary outcome) at the intervention hospital preversus post-implementation of the Code Sepsis protocol using the measured change at non-intervention hospitals to control for pre-/post-intervention changes not attributable to protocol implementation.

 $Y_i = \beta_1 \text{ERA}_i + \beta_2 \text{HOSP} + \beta_3 \text{ERA}_i \times \text{HOSP}_i + \beta_4(Z_i)$ Figure 5. Simplified difference-in-differences equation.  $Y_i$  is the door-toantibiotic time for patient *i*, HOSP and ERA are, respectively, indicator variables for care at the intervention hospital or an ED arrival date after Code Sepsis implementation, and Z is a vector of covariates.  $\beta_3$  is the coefficient of interest.

This model tests the *difference* in intervention ED versus non-intervention EDs' *differences* in outcome before versus after the Code Sepsis implementation (Figures 4-5). The  $\beta_3$  parameter from the regression model depicted in Figure 5

provides the adjusted difference-in-differences estimate and significance tests for the influence of the Code Sepsis intervention on the outcome of interest.

#### 7.2 Multivariable models

Multivariable models will be adjusted for demographic and clinical parameters with known or plausible associations with both door-to-antibiotic time and treatment hospital, presentation before or after Code Sepsis implementation, and/or Code Sepsis activation. Evaluation of secondary outcomes will employ an analogous approach using multivariable linear, Poisson, or logistic regression as appropriate. Repeating the quasi-experimental analysis for the primary and key secondary outcomes after stratification (rather than adjustment) by (1) sex and (2) hypotension present versus absent on ED arrival will allow evaluation of whether these patient characteristics modify the effects of Code Sepsis implementation. In order to measure how the Code Sepsis protocol influences the care of its core target population, we will perform analyses comparing selected outcomes among the subset of patients who have ED triage data suggesting a strong possibility of sepsis. Outcomes to be evaluated in the sensitivity analyses will include door-to-antibiotic time, antibiotic treatment fraction, and antibiotic treatment spectrum.

#### 7.3 Sample size/power analysis

Using 2013 to 2017 data from our study hospitals, we estimated conservatively that the intervention ED provides care for 1,650 sepsis patients annually (approximately 4.5 sepsis patients per day) and the

control EDs together care for a total of 2,200 sepsis patients annually (approximately 6 sepsis patients per day). Based on the design and our pilot testing of the Code Sepsis protocol, a very conservative estimate of door-to-antibiotic time for patients who receive antibiotics after evaluation under the Code Sepsis protocol is 50 minutes. By comparison, our preliminary data from 2013 to 2017 indicates current mean (SD) door-to-antibiotic time for ED sepsis patients is 170 (±75) minutes and that only 5% of patients currently receive antibiotics within 1 hour of ED arrival. Assuming (again conservatively) that the Code Sepsis protocol is activated for 30% of sepsis patients treated in the intervention ED during the full implementation phase (study phase #3), we will have 90% power to detect a difference-in-differences change of 16 minutes or more in door-to-antibiotic time associated with Code Sepsis implementation, with the measurement population being all ED sepsis patients. Power calculations employed Monte Carlo simulations, for which technical details are available upon request.

### 8. RISK ASSESSMENT

This study involves a before-and-after analysis of the effects of reorganizing standard ED care for sepsis. Patient care will be studied under two designs for standard sepsis care.

#### 8.1 Potential Risks

#### 8.1.1 Risk of confidentiality breach

Potential consequences of a breach of confidentiality to the subject could include identify loss of privacy, medicolegal liability, theft, embarrassment, or harassment.

#### 8.1.2 Risks for control group patients

Aside from issues discussed above, there are no foreseeable risks for ED patients receiving care at a nonintervention hospital or at the intervention hospital during study phase #1 and #2. Sepsis patients arriving to control hospitals will receive standard care throughout the study.

#### 8.1.3. Risks to patients exposed to the Code Sepsis protocol

Patients presenting to the intervention hospital during phases #2 and 3 (run-in implementation and full implementation) will be exposed to and may receive care using the "Code Sepsis" version of standard care. The Code Sepsis protocol is designed to accelerate evaluation, testing, and treatments that the patient would have eventually received under now current standard care. The Code Sepsis intervention is therefore expected to pose no more than minimal risks to ED patients exposed to the protocol, including specifically sepsis patients for whom the Code Sepsis protocol is activated. The potential risks to subjects due to this protocol include:

- 1) Adverse drug reactions or antibiotic-associated infections related to unnecessary or overtreatment antibiotic treatment with prespecified regimens.
- 2) Delay in diagnosis of non-infectious problems due to focus on sepsis or infection related to Code Sepsis activation.
- 3) Delay in care related to resource allocation away from non-Code Sepsis patients without sepsis (bystanders without sepsis).
- 4) For sepsis patients for whom the Code Sepsis protocol is not activated (i.e. bystanders with sepsis), delay in care related to lower index of suspicion for sepsis leading to delayed diagnosis or resource allocation away from these patients.

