#### 2.4 Study Design

Pragmatic phase 2a pre/post single-center implementation study with contemporaneous controls testing reorganization of standard ED sepsis care around a protocol for early, coordinated, multidisciplinary protocol for assessment of patients with potential sepsis (Code Sepsis protocol).

- 1. We will emphasize pragmatic, real-world implementation of the Code Sepsis protocol in a single ED.
- 2. We will compare care delivered to ED patients after Code Sepsis protocol implementation in the intervention ED to care received in this ED prior to Code Sepsis implementation.
- 3. We will conduct a quasi-experimental analysis using contemporaneous control data obtained from two non-intervention hospitals to control for temporal trends in studied outcomes not resulting from the tested intervention.
- 4. We will measure the effects of protocol implementation on all ED patients with sepsis (including patients not treated under the Code Sepsis protocol) as well as potential bystander effects.

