#### 3.7.1 Primary outcome

Door-to-antibiotic time among all ED sepsis patients. Door-to-antibiotic time is the time from the first recorded arrival time in ED (usually ED triage or registration) and the time the first eligible antibiotic was administered (Appendix A).

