    - Organ-failure free days (OFFD) are defined as the number of days from the time of the first SOFA score ≤1 above baseline to day 28 after ED arrival, assuming survival for at least two consecutive calendar days after the SOFA score ≤1 above baseline and continued SOFA score ≤1 point above baseline to day 28. If a patient has SOFA score rise again to ≥2 points above baseline and subsequently achieves SOFA score ≤1 point above baseline to day 28, VFDs will be counted from the end of the last period of SOFA score ≤1 to day 28. If a patient had SOFA score ≥2 points above baseline at day 27 or dies prior to day 28, OFFD will be zero
    - Support-free days (i.e. ventilator-free days) are calculated similar to OFFD
  - 2) Mortality at other intervals
  - 3) Testing and treatment utilization. Outcomes measured among (1) among all ED sepsis patients;
    (2) all ED patients; (3) "likely" sepsis patients
  - 4) Code Sepsis care process timing: measured among patients who received Code Sepsis protocol activation as time from protocol activation until completion of key protocol steps, to include blood culture collection, chest X-ray collection, team huddle, antibiotic initiation
  - 5) Timing of testing & care processes among all sepsis patients, to include ED clinician assessment, ED room placement, ED departure, blood culture collection, radiology testing, and order entry for antibiotics. Measured analogous to door-to-antibiotic time.
  - 6) Code Sepsis protocol adherence: measured as performance of protocol steps in correct order both individually and as a fraction of all possible.

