#### 10.5 Data and Safety Monitoring

Given that this study is using pre-post method to study implementation of a method to deliver clinical standard-of-care therapies in a more efficient, expeditious, and coordinated manner, the safety monitoring plan will be implemented with the use of an *Independent Safety Monitor (ISM)*. The ISM will monitor participant safety, evaluate the progress of the study, review procedures for maintaining the confidentiality of data, and monitor the quality of data collection, management, and analyses. The PI and study personnel will provide all necessary and requested reports to the ISM in a timely manner. The ISM will have full capacity to end the study at her/his discretion if there is an important safety signal, according to a safety monitoring charter that will be finalized in consultation with NIH and the ISM before study launch. Notably, given that the "intervention" in this trial is a non-randomized implementation of a bundle of timely care for sepsis treatment, the safety monitoring plan will focus on monitoring the Code Sepsis activations. The PI will be responsible for ensuring participants' safety and that the study is conducted according to the IRB-approved research plan on a daily basis.

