limited in that it only considers the control and treated groups during the pre-implementation phase. If the pre-test of parallel trends assumption fails, then we will weight the gamma regression model with propensity scores. As demonstrated by Stuart *et. al*, this will balance the covariates amongst the four study groups defined by their treatment status as well as time (pre vs post). We will leverage the covariate balancing propensity score (CBPS) library in R to generate propensity scores. This weighting approach can recover treatment effects in that it allows for adjustments due to observed baseline covariates that differ either across groups or over time. Covariates that will be used in generating propensity scores will include age; sex; weighted Elixhauser comorbidity score; English language preference; first-available heart rate, temperature, systolic blood pressure, and respiratory rate; acute physiology score; ED arrival at nightime (10 pm to 6:59 am), ED arrival on weekend (midnight Saturday to 11:59 pm Sunday), SARS-CoV-2 test result (positive, negative, or not performed during ED-associated hospitalization or within 14 days preceding ED arrival); and insurance type. For analyses involving a cohort of patients with sepsis, propensity score covariates will additionally include arrival to ED via ambulance; presentation from a long term care facility; serum lactic acid level checked and ≥2 mmol/dL; ED SOFA score; and ED-diagnosed infection source.

In order to account for the right skew known to exist in door-to-antibiotic time we will use generalized linear gamma regression to estimate the DID. Evaluation of secondary outcomes will employ an analogous approach using multivariable linear, Poisson, logistic, or gamma regression as appropriate. Data from the wash-in phase will be excluded from DID analyses. All multivariable models will be adjusted for demographic and clinical parameters with known or plausible associations with both outcomes and treatment hospital, presentation before or after Code Sepsis implementation, and/or Code Sepsis activation as well as select precision variables as detailed below. Analyses for secondary, safety, and heterogeneity of treatment effect outcomes will not be adjusted for multiple comparisons and will therefore be considered hypothesis generating.

Statistical significance will be set to p < 0.05. All analyses will be conducted with R.

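### Delay to bystanders is a named risk that the study undertakes to measure, yet no outcome times care in ED patients without sepsis, and sepsis patients without activation are seen only in a pooled mean or through proxy subgroups

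*Protocol*

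**What the plan says.** Protocol 8.1.3 lists two bystander risks. One is delay for patients without sepsis because resources go to Code Sepsis patients. The other, for sepsis patients without an activation, is "delay in care related to lower index of suspicion for sepsis leading to delayed diagnosis or resource allocation away from these patients". Protocol 2.4 (item 4) says the study will measure effects on all ED sepsis patients "as well as potential bystander effects", so bystander effects are promised in addition to the all-sepsis result. The protocol's section on anchoring bias (the second one numbered 8.3.4) accepts that many sepsis patients will not trigger an activation.

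The outcomes then run as follows.

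- **Primary (Protocol 3.7.1):** "Door-to-antibiotic time among all ED sepsis patients", with activated and non-activated patients pooled. The SAP uses the same cohort.
- **Care timing (Protocol 3.7.2, potential exploratory outcomes):** "Timing of testing & care processes among all sepsis patients", so sepsis patients only. The item that reaches all ED patients concerns use of tests and treatments, not timing. The SAP outcome tables carry neither forward.
- **SAP Safety outcomes:** antibiotic use and spectrum, adverse reactions, *C. difficile*, overtreatment of sepsis mimics, and false-positive infection diagnosis. None is a time to care.
- **SAP Process outcomes:** activation sensitivity counts the sepsis patients who were missed, but not how long they waited.
- **Monitoring (Protocol 10.5):** "the safety monitoring plan will focus on monitoring the Code Sepsis activations". The case reviews in 8.3, 10.2.3 and 10.5.1 (item 2) are of activated patients. Protocol 10.5.1 (item 1) adds ED-wide incident review, with monthly contact with the ED medical director and control-ED comparison if needed.

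**The concern.** The study names a harm and undertakes to look for it, but following the plan as written leaves half of that question unanswered and the other half answered only indirectly. For patients without sepsis there is no timing outcome at all. For sepsis patients without activation, any delay is netted against the gain in activated patients, so a favourable average cannot show whether the second risk occurred. Incident review has no timing measure, and modest average delays need not generate incident reports.

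Protocol 3.5 and section 5 tie continuation of the protocol, and its spread within the health system, to these results. That decision would be taken without direct evidence on a risk that the protocol itself lists.

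**Working it through.** **Inputs.** Protocol 7.3 states that "current mean (SD) door-to-antibiotic time for ED sepsis patients is 170 (±75) minutes". It also gives 1,650 sepsis patients a year at the intervention ED and 2,200 at the control EDs, 30% of intervention-ED sepsis patients activated, and 50 minutes to antibiotics under the protocol. SAP, Data analysis: "Statistical significance will be set to p < 0.05", read as two-sided because the test is for a difference from zero. Protocol 4.1: 89,000 annual visits at the intervention ED, 2.8% with clinical sepsis.

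**The plan's own figure.** The plan claims "90% power to detect a difference-in-differences change of 16 minutes or more in door-to-antibiotic time". With four independent means, SE = 75 × √(2/1650 + 2/2200) = 3.45 minutes. That gives 99.6% power at 16 minutes, and 90% power at 3.24 × 3.45 = 11.2 minutes. So 90% is not reproduced. It would need an SE of 16/3.24 = 4.94 minutes, for example through site-by-period variance. The simulation details are not given. The stated figure is on the cautious side and the point does not depend on it.

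**How much delay the mean can absorb.** Let p be the share activated, b the mean time activated patients would have had without the protocol, and d the mean delay in the rest. The net reduction is p(b − 50) − (1 − p)d. Setting this to 16 gives d = [p(b − 50) − 16]/(1 − p).

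| p | b (min) | Reduction if d = 0 | d leaving a 16-minute benefit |
|---|---|---|---|
| 30% | 170 | 36 | 20/0.70 = 28.6 |
| 30% | 150 | 30 | 14/0.70 = 20.0 |
| 30% | 130 | 24 | 8/0.70 = 11.4 |
| 30% | 110 | 18 | 2/0.70 = 2.9 |
| 20% | 170 | 24 | 8/0.80 = 10.0 |
| 40% | 170 | 48 | 32/0.60 = 53.3 |

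The documents do not give b; 170 is the mean for all sepsis patients. In the first row, the chance of declaring a benefit despite the delay is 90% at the SE of 4.94 implied by the protocol. Under the simple model the post-period SD is √(75² + 0.21 × 148.6²) = 101.3, the SE is 3.84, and the chance is 98.6%.

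**The 3-hour outcome.** Assumptions: gamma times with the same coefficient of variation as 170/75, the overall baseline held at 170, activated patients at mean 50 and SD 20 under the protocol, and a fixed 28-minute delay in the other 70%. Mean change = −0.30(b − 50) + 0.70 × 28.

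| b (min) | Mean change (min) | Share treated within 3 hours, before → after |
|---|---|---|
| 170 | −16.4 | 60.9% → 62.2% |
| 150 | −10.4 | 61.1% → 59.3% |
| 130 | −4.4 | 61.4% → 56.6% |
| 110 | +1.6 | 61.3% → 54.1% |

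The 3-hour share moves the wrong way at every shorter baseline and looks neutral only at 170.

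**Patients without sepsis.** They are 100 − 2.8 = 97.2% of intervention-ED visits and contribute nothing to either calculation. No arithmetic on the planned timing outcomes can speak to them.

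**The case against.** The all-sepsis mean is a deliberate and valid estimand: it includes non-activated sepsis patients, as do the mortality outcomes, so their delay is netted in, not left out. The SAP's heterogeneity analyses go further. Ambulance arrival, hypotension on arrival and acute physiology score (APS) quartile are defined in all four site-by-period groups without conditioning on activation. Because activation comes from prehospital calls, triage or room placement (Protocol 5.2), walk-in, non-hypotensive and low-score patients are plausible low-activation strata. ED-wide incident review exists, comparison with control EDs is possible, and Protocol 8.3 allows the intervention to be adjusted or halted. Protocol 10.5 also refers to a monitoring charter that is not among the documents reviewed. All of this stands. The subgroups are still proxies, and none of it times care in patients without sepsis.

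A reader might infer four stronger things that the documents do not support.

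- *That nothing separates sepsis bystanders from activated patients.* The proxy subgroups do so in part.
- *That a 28.6-minute delay is likely.* It is an upper figure under one baseline, and patients recognised early as likely septic may well have been treated faster than average anyway.
- *That the 3-hour outcome would miss the harm.* That holds only at the 170-minute baseline.
- *That most of the ED will wait longer.* At 30% of 1,650 a year there are about 495/365 = 1.4 activations of sepsis patients a day among 89,000/365 = 244 visits. False activations add to that, but no displacement estimate exists.

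**Conclusion.** The gap is real and should be closed. It is clearest for ED patients without sepsis: delay to them is a named risk, its measurement is promised, and no outcome in either document can show it. For sepsis patients without activation the gap is partial, because their experience enters the primary result and can be glimpsed through the proxy subgroups, but no analysis isolates it.

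The size depends on figures the documents do not give. At 30% activation, a 16-minute net benefit is compatible with a mean delay of 2.9 to 28.6 minutes in the other 70%, as the activated patients' untreated baseline runs from 110 to 170. At the 170-minute baseline the figure is 10.0 minutes at 20% activation and 53.3 at 40%. These show what the pooled mean can conceal, not what is expected. The statement about monitoring applies to these two documents only. The primary analysis itself is not called into question.

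**What to change.** **(a) Patients without sepsis.** Add to the SAP safety outcomes the planned DID on arrival-to-room time, arrival-to-clinician time and ED length of stay, in `cohort_all` patients who are not in `cohort_sepsis`. Protocol 6.5 already lists room placement, provider interaction and ED length of stay. Keep patients with an activation but no sepsis in this group: removing them only after implementation at one site would condition on activation. Include these measures descriptively in the quarterly report to the safety monitor.

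**(b) Sepsis patients, as a supporting analysis.** Model activation from triage data and arrival mode in phase 3 at the intervention ED, and apply the model to all four site-by-period groups. Run the door-to-antibiotic DID among patients with low predicted activation, with the cut-off fixed in advance. Read it beside the existing ambulance, hypotension and APS subgroups. A direct split on activation is not enough, because pre-period patients have no activation status and those not activated later are a selected group. As a rough guide to precision, a contrast using all 0.70 × 1,650 = 1,155 non-activated patients after implementation has SE = 75 × √(1/1650 + 1/1155 + 2/2200) = 3.66 minutes. That is 90% power for 11.9 minutes, or 17.0 if scaled to the protocol's own 16 (16 × 3.66/3.45). The low-probability stratum will be smaller and needs its own calculation.

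**Interpretation.** State that a positive coefficient signals possible bystander delay and does not prove it. There is one intervention site, and the post period (February 2020 to February 2021) may carry site-specific changes in volume and staffing.

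**Cost.** A few paragraphs of SAP text and extra model runs on data already listed for collection. The downside is several more comparisons unadjusted for multiplicity, to be labelled exploratory, and some activated patients will remain in stratum (b).
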